#### 9.2 Potential Risks

Possible risks, side effects, and discomforts include:

Risk	Likelihood	Consequences
ViMove not registering body movements	Low	Device will warn the health care professional (HCP) and subject that it can no longer
		provide assessment. If this occurs during a monitoring session you need to inform your HCP immediately.
Possible irritation of the skin from wearing ViMove	Low	Low Skin Itching and/or discomfort for up to 8 hours.
ThermaCare related issues	Low	Skin reactions to ThermaCare. This may include itching. Subjects may also be sensitive to heat.

ViMove has undergone rigorous verification, validation, user acceptance and post market testing and is not expected to malfunction. However, anyone participating in this study who has concerns about the safety or other functioning of ViMove should report them immediately to the investigative team.

### 9.2.1 Risk Minimization

Ensuring the safety of participants is of upmost importance. As such, numerous protocols and procedures will be in place to minimize the risk of harm.

- Strict adherence to the eligibility criteria is the foremost step in mitigating any potential harm.
- Participants are also permitted to withdraw consent for any reason at any point in the trial.
- Protocol for recording, reporting and follow-up of any adverse effects.
- Selection of qualified investigators and site personnel.
- Stringent training of investigative staff, regarding the use of questionnaires and devices.
  - This includes training of ViMove fitment and assessment.
- ThermaCare usage has a risk of prolonged skin redness or burns for some people. Products will be applied and used as directed.

### 10: SAFETY CONSIDERATIONS

An Adverse Event (AE) is any undesirable clinical occurrence in a Subject whether or not it is related to ThermaCare or ViMove. This includes a clinical sign, symptom, condition, and/or an observation of an unintended therapeutic effect.

An Adverse Device Event is a clinical sign, symptom or condition that is caused by the presence of the device or the performance of the device system.

A Serious Adverse Event (SAE) is an occurrence of: death, a life-threatening adverse event, inpatient hospitalization or prolongation of existing hospitalization, or a persistent or significant incapacity or substantial disruption of the ability to conduct normal life functions.

# 10.1 Documentation and Reporting of Adverse Events

All participants will be evaluated and monitored for AEs from recruitment. Once onset of an AE has been determined, evaluation will continue until its resolution is observed, or until the investigator determines that the subject's condition is stable. The investigator will take appropriate and necessary therapeutic measures required for the resolution of the AD. Any medication necessary for the treatment of an adverse event must be recorded on the concomitant medication case report form.

All AEs, regardless of severity, will be recorded in the source documents and CRFs using standard medical terminology. Colloquialisms and/or abbreviations should not be used. Only one medical concept, preferably a diagnosis rather than individual symptoms, should be recorded as the AE.

If more than one distinct adverse event occurs, each event should be recorded separately. However, if a diagnosis (i.e., disease or syndrome) is known at the time of reporting, it should be recorded on the CRF rather than recording individual signs and symptoms (e.g. record congestive heart failure rather than dyspnea, rales and cyanosis). However, if a group of signs and/or symptoms cannot be medically characterized as a single diagnosis or syndrome at the time of reporting, each individual event should be recorded as a separate AE. A diagnosis that is subsequently established should be reported as follow-up information. However, signs and symptoms that are considered unrelated to an encountered syndrome or disease should be recorded as individual AEs (e.g. if congestive heart failure and severe headache are observed at the same time, each event should be recorded as an individual AE).

Conditions or diseases that are chronic but stable should not be recorded on AE pages of the CRF but should be recorded on the medical history. Changes in a chronic condition or disease that are consistent with natural disease progression do not need to be recorded as adverse events and should not be recorded on the AE pages of the CRF.

Adverse events occurring secondary to other events (e.g. sequelae) should be identified by the primary cause. A "primary" event, if clearly identifiable, should represent the most accurate clinical term to record as the AE event term. For example: Orthostatic hypotension, fainting and fall to floor, head trauma, neck pain. The primary event is orthostatic hypotension and the sequelae are head trauma and neck pain.

AE grading and severity are as follows:

Grade 1	MILD	Transient discomfort; no medical intervention/therapy required and does not interfere with daily activities.
Grade 2	MODERATE	Low level of discomfort or concern with mild to moderate limitation in daily activities; some assistance may be needed; minimal or no medical intervention/therapy required.
		Extreme discomfort and limitation in daily activities; significant assistance required; significant medical intervention/therapy required.
Grade	SEVERE	Note: There is a distinction between the severity and the seriousness of an adverse event.
3		Severity is a measurement of intensity; thus, a severe reaction is not necessarily a serious adverse event (SAE). For example, a headache may be severe in intensity, but would not be serious unless it met one of the criteria for serious adverse events.
Grade 4	POTENTIALLY LIFE-THREATENING OR DISABLING	AE that is potentially life-threatening or may lead to a permanent disability.
Grade 5	FATAL	AE that leads to death.

The relationship of an AE following the use of the devices (ThermaCare or ViMove) is classified as follows:

UNRELATED	
 
Evidence indicates no plausible direct relationship to the devices such that:
 
A clinically plausible temporal sequence is inconsistent with the onset of the AE and device administration, and/or
 
A causal relationship is considered biologically implausible
 
The AE can be attributed to concurrent/underlying illness, other drugs or procedures.
 

POSSIBLY RELATED	1. The event occurs within a reasonable period of time relative to the treatment that makes a causal relationship possible, but plausible explanations may also be provided by other causes such as other drugs, products, chemicals, underlying disease, environment, etc.  2. The event is possibly related to either of the devices.

RELATED	Evidence indicates a reasonable temporal sequence of the event with device administration exists or that the association of the event with device administration is unknown and the event is not reasonably supported by other conditions such that:  1. There is a clinically plausible time sequence between onset of the AE and device administration, and/or  2. There is a biologically plausible mechanism for the device causing or contributing to the AE, and  3. The AE cannot be reasonably attributed to concurrent/underlying illness, other drugs or procedures.
---------	--

The outcome of the AE is classified as one of the following:

RESOLVED	All symptoms associated with the AE have subsided.
ONGOING	Subject continues to experience some or all of the symptoms associated with the AE.
FATAL	Subject died as a result of the AE.

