# 8.5.2 ViMove – Pain on movement

Pain on movement compares subjective responses of pain, with objective movement data from ViMove sensors. Assessment requires subjects to move within a maximum tolerable range. A numeric pain rating scale (see below) will be used during each movement, to obtain a value for the level of pain that each subject experiences. Consistent and standardized instructions are used, with the pain scores being recorded in the ViMove system. If no pain on movement is reported, a score of 0 will be documented.

(No Pain) 0 1 2 3 4 5 6 7 8 9 10 (Worst Pain)

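### The causality scale in 10.1 pools ThermaCare and ViMove and has no place for the study's own assessments, so on Day 2 the rating alone cannot identify wrap-related or assessment-related events

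*Combined protocol and SAP*

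**What the plan says.** The relationship table in section 10.1 is introduced by "The relationship of an AE following the use of the devices (ThermaCare or ViMove) is classified as follows" and has three levels: UNRELATED, POSSIBLY RELATED and RELATED. One condition listed under POSSIBLY RELATED is "The event is possibly related to either of the devices". One of the UNRELATED conditions is "The AE can be attributed to concurrent/underlying illness, other drugs or procedures", and the mirror condition under RELATED is "The AE cannot be reasonably attributed to concurrent/underlying illness, other drugs or procedures". Nothing in the protocol asks for a separate rating per device or for the suspected device to be named, and no level refers to the study's own assessments.

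Section 10 defines an AE as any undesirable clinical occurrence "whether or not it is related to ThermaCare or ViMove". Section 10.1 adds that "All AEs, regardless of severity, will be recorded in the source documents and CRFs using standard medical terminology".

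On exposure, section 8.4 has participants wear ViMove without the wrap on Day 1, and the wrap together with the ViMove sensors for the 8-hour monitoring period on Day 2. Section 8.5.1 has the sensors attached to lumbar skin with adhesive pads. The risk table in 9.2 lists skin itching or discomfort for ViMove, and for the wrap "Skin reactions to ThermaCare. This may include itching". For the in-clinic tests, section 8.5.2 says "Assessment requires subjects to move within a maximum tolerable range", and section 4 adds lift-and-carry, squatting and sit-to-stand tasks.

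**The concern.** Sections 8.2 and 11.1 describe a feasibility study meant to inform a later randomised trial. A trial of the wrap would need to know how often the wrap itself causes a reaction, and how often the assessment battery provokes symptoms in people who enter with back pain. A pooled device rating answers neither question.

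The pooling matters most on Day 2, the only day on which the wrap can cause harm. A second, sensor-based source of similar skin symptoms is then on the same part of the body. Section 11.2 specifies no safety analysis that would separate the sources afterwards, and a causality judgement not captured at the time is hard to reconstruct.

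**Working it through.** The documents give no AE rates, and the plan has no figure of its own on this point. The one derivable design figure is the recruitment target: 40 / (1 − 0.20) = 50, as sections 6 and 11.1 state. The point does not depend on it. The check is a comparison of sections.

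**Step 1. Which device could cause a skin event, by time (section 8.4 and Table 1).**

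| Period | Wrap on | Movement sensors on | Possible device cause |
|---|---|---|---|
| Day 1, Visit 2 to Visit 3 | No | Yes | Sensor only |
| Visit 4, before the wrap is applied | No | Yes | Sensor only |
| After wrap application at Visit 4, to Visit 5 | Yes | Yes | Wrap, sensor or both |

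Section 8.4 says the wrap is not worn at the same time as the EMG sensors, so the overlap concerns the movement sensors. Only the last row is ambiguous, but it is also the only row in which the wrap can act.

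**Step 2. What the rating tells us in that last row.** Suppose k of the 40 planned participants have a Day 2 skin event rated POSSIBLY RELATED or RELATED. The rating does not say to which device. From the rating alone, the number with a wrap reaction can be anything from 0 to k, so the wrap rate lies between 0 and k/40. For assumed values of k:
- k = 1: 0 to 1/40 = 2.5%
- k = 2: 0 to 2/40 = 5%
- k = 5: 0 to 5/40 = 12.5%

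These counts only illustrate the width of the interval. They are not estimates.

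**Step 3. Whether another rule recovers the device.** Section 10.3 asks for a device serial number, but only for malfunctions, technical problems or operator error. A skin reaction to a correctly working device is outside it. Event terms and timing are collected under 10.1 and Table 1 and will narrow some cases, but neither is a device attribution.

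**Step 4. How an assessment-provoked flare would be rated.** In-clinic assessments take place at Visits 2 to 5, four per participant: 40 × 4 = 160 in total, of which 20 × 4 = 80 are in the low back pain group. Two readings of the table are open:
- If the tests count as procedures within "The AE can be attributed to concurrent/underlying illness, other drugs or procedures", the flare can be rated UNRELATED, and it fails the mirror condition for RELATED.
- If *other* is taken to mean procedures outside the study, or the tests count as use of ViMove, the flare can be rated POSSIBLY RELATED or RELATED. It is then pooled with wrap and sensor reactions.

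Under neither reading does the rating identify the event as caused by a study assessment.

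**The case against.** The strongest reply is that nothing is lost from the record. AEs are recorded whatever their relationship to the devices, and section 10.2 requires all serious events to be reported. That stands. A reader might infer that test-provoked flares disappear from the safety data, and the documents do not support this: an UNRELATED rating removes an event only from a device-related tally. The rule in 10.1 that can keep events off the AE pages concerns natural progression of chronic conditions, and it does not depend on the causality rating.

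Second, Day 1 is a ViMove-only day and AEs are collected at Visits 2 to 5. A reader might infer that wrap and sensor reactions can never be told apart. That is too strong, because events arising before the wrap is applied cannot be due to it. Some Day 2 events may also point to their cause: section 9.2.1 names prolonged redness and burns as wrap risks. This confines the problem to Day 2 but does not remove it there. Day 2 is also the second consecutive day of sensor wear, so the Day 1 sensor rate need not carry over.

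Third, the phrase about procedures is ambiguous, and section 4 treats the movement tests as part of the ViMove assessment. It would be wrong to say that the plan directs flares to be rated UNRELATED; it permits this. Nor can it be said that the related-event rate will be too low, since the opposite reading pools flares into it.

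Finally, the AE CRF is not among the documents. It may already have a field for the suspected device.

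**Conclusion.** The point holds in a limited form and should be corrected. As written, the scale gives one rating per AE for two devices and does not say how to rate events caused by study assessments. On Day 2, wrap reactions cannot be told from sensor reactions by the rating alone, and assessment-provoked events cannot be identified by it on either day. This weakens the tolerability information available for a later trial. It does not affect the completeness of AE recording or the reporting of serious events.

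The scope is one 8-hour wrap day for each of 40 planned participants, and 160 in-clinic assessments. How many events are affected cannot be estimated from the documents. The conclusion assumes that investigators follow the table as printed and that the CRF adds no device field. If it has one, the first part shrinks to making that field a protocol requirement.

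The absence of test-provoked pain from the 9.2 risk table is a separate documentation matter, and this conclusion does not rest on it.

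**What to change.** In section 10.1 and on the AE CRF:

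1. Replace the single rating with three per AE: relationship to ThermaCare, to ViMove (sensor or adhesive), and to study assessments.
2. In both the UNRELATED and RELATED conditions, replace the reference to procedures with *procedures not required by this protocol*.
3. For each skin event, record the site (under the wrap, under a sensor pad, or both) and whether it was already present at Visit 4 before the wrap was applied. AE collection is already scheduled at that visit.

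The cost is a revised table and a few extra CRF fields, with no added visits or participants. A few more events will be labelled related, because assessment-provoked events will have a category of their own.

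### The adverse event outcome table counts symptoms only, so a visible but painless skin reaction to the wrap is coded RESOLVED, and such a sign fits none of Grades 1 to 3 as worded

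*Combined protocol and SAP*

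**What the plan says.** Section 10 defines an adverse event (AE) broadly: "This includes a clinical sign, symptom, condition, and/or an observation of an unintended therapeutic effect". A sign alone is therefore enough. Section 9.2.1 names the harm expected from the wrap: "ThermaCare usage has a risk of prolonged skin redness or burns for some people". The risk table in Section 9.2 adds skin reactions, which may include itching, and sensitivity to heat, all rated low in likelihood.

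The outcome table in Section 10.1 has three categories. RESOLVED is "All symptoms associated with the AE have subsided". ONGOING is "Subject continues to experience some or all of the symptoms associated with the AE". The third is FATAL.

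The grading table in the same section defines Grade 1 as "Transient discomfort; no medical intervention/therapy required and does not interfere with daily activities", Grade 2 as "Low level of discomfort or concern with mild to moderate limitation in daily activities; some assistance may be needed; minimal or no medical intervention/therapy required" and Grade 3 as "Extreme discomfort and limitation in daily activities; significant assistance required; significant medical intervention/therapy required". Grade 4 rests on threat to life or possible permanent disability, and Grade 5 on death.

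On follow-up, Section 10.1 states that "evaluation will continue until its resolution is observed", or until the investigator judges the condition to be stable. It requires every AE to be recorded whatever its severity. In Table 1 (Section 8.4), removal of the wrap and study termination both fall at Visit 5, the last scheduled visit.

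**The concern.** The definition of an AE and the table that classifies its outcome use different terms. The definition separates signs from symptoms; the outcome table mentions only symptoms. Redness is something staff see, and its persistence is what makes it a harm in Section 9.2.1. Once it no longer hurts or itches, the outcome table has nothing left to count.

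What is at stake is the safety record for a harm that the protocol itself names. A reaction still on the skin could be listed as resolved, its duration would look shorter than it was if read from that code, and its grade would depend on an unwritten judgement. Sections 8.2 and 11.1 say the study is to inform a randomised trial, and the length and severity of heat reactions are among the things that the next protocol would want to know.

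**Working it through.** The plan gives no figure on this point, so there is none to reproduce. The check applies the written definitions literally.

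**Step 1: outcome.** Inputs are the AE definition (Section 10) and the outcome table (Section 10.1). Four states are possible for a non-fatal skin AE:

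| Sign still visible | Symptom still felt | Code as written | Agrees with the AE definition? |
|---|---|---|---|
| Yes | Yes | ONGOING | Yes |
| No | Yes | ONGOING | Yes |
| No | No | RESOLVED | Yes |
| Yes | No | RESOLVED | No |

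One state of the four is miscoded, and it is the one that describes lasting redness without discomfort. No category exists for a stable or residual sign, although Section 10.1 allows evaluation to end when the condition is stable.

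**Step 2: grade.** Take a visible lesion with no discomfort, no activity limitation and no threat to life. Allow that it causes concern, which is the reading most favourable to Grade 2.

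| Grade | Element that fails | Elements that can be met |
|---|---|---|
| 1 | Discomfort, and that it be transient | No intervention; no interference with activities |
| 2 | Activity limitation | Concern; minimal or no intervention |
| 3 | Extreme discomfort, activity limitation and significant assistance | Significant intervention |

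Crossing three levels of intervention (none, minimal, significant) with possible permanent disability (no, yes) gives 3 × 2 = 6 cases. In the three cases without possible permanent disability, no grade is met. In the three cases with it, Grade 4 is met.

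**Step 3: does the gap lose the event or end its follow-up?** Section 10.1 requires all AEs to be recorded, so the event is kept. Evaluation runs until resolution is observed or the condition is stable, and the text does not say that resolution for this purpose is the RESOLVED category of the outcome table. The follow-up rule and the outcome table can therefore disagree about when a skin AE is over, but the outcome table is not stated to be the stopping rule.

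**Step 4: frequency.** Section 9.2 gives only a low likelihood for wrap-related problems, with no rate, and nothing on the share that would be visible but painless. No event count can be derived.

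**The case against.** The strongest reply is that Section 10.1 uses the word symptoms loosely. In one place it prefers a diagnosis to individual symptoms, and in the next paragraph makes the same point about signs and symptoms, with examples that include signs. On that usage, visible redness would count as not yet subsided, and few investigators would call a recorded burn resolved while they could see it. This softens the point but does not remove it. Section 10.1 otherwise writes signs and symptoms together, and ONGOING requires that the subject continue to experience something, which a painless mark does not satisfy.

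Several stronger readings are tempting, and the documents do not support them:

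- A reader might infer that follow-up of a skin reaction is necessarily closed early. Section 10.1 also lets evaluation run until the condition is stable, and does not tie it to the outcome table.
- A reader might infer that no painless skin injury can be graded. Grading also uses need for intervention, Grade 2 admits concern, and Grade 4 covers possible permanent disability. Painless redness that needs no treatment meets two of the three Grade 1 elements, so Grade 1 is the likely choice in practice.
- A reader might infer that this affects most heat-related events. Burns and itching are also named, itching is a symptom that the tables handle, and no rate is given for any of these.
- A reader might infer that a planned result would change. Sections 11.2, 13.1 and 13.2 contain no analysis or endpoint based on AE grade, outcome or duration.

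The last objection stands in full: this is a fault in the safety record and does not touch the efficacy analysis.

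**Conclusion.** Wrong as written, and small in scope. The outcome table does not match the AE definition in Section 10: a visible skin reaction with no remaining discomfort is coded RESOLVED and cannot be coded ONGOING. A painless sign with no activity limitation and no risk of permanent disability also falls outside the wording of Grades 1 to 3, though Grade 1 would probably be used. The consequence is a misclassified outcome, duration and grade for a recorded event. No event is lost, and early closure of follow-up is possible but not implied.

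The conclusion rests on reading the tables as written and on duration being judged from the outcome code. Its frequency cannot be estimated from the documents. The point is still worth correcting, because Section 9.2.1 names this kind of harm and the wrap comes off at the last scheduled visit, so no later scheduled visit would put a wrong code right.

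**What to change.** Reconcile the outcome table in Section 10.1 with the AE definition in Section 10 and the follow-up text in Section 10.1, so that RESOLVED and ONGOING both refer to signs and symptoms. Reconcile the grading table with the same definition, so that a sign without discomfort has a grade.

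These edits concern how events are classified. They change nothing about how the wrap is used or how a reaction is managed. The wording should not depend on comparison with the skin before the wrap, because neither Section 8.4 nor Table 1 schedules a skin inspection at that point.

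The cost is a few words in two tables, with no added visit, staff or procedure; any follow-up after Visit 5 is already provided for in Section 10.1. The downside is that a few reactions will be listed as ongoing for longer.
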